**THE EFFECT OF ORAL ATORVASTATIN ON MICROVASCULAR
ENDOTHELIAL FUNCTION AND RAYNAUD PHENOMENA IN EARLY DIFFUSE
SYSTEMIC SCLEROSIS (TAMER)**

Atorvastatin on endothelial function and Raynaud in diffuse scleroderma

Test drug: Atorvastatin

Study purpose: Safety and efficacy

Clinical study phase: II

Sponsor: University of Pittsburgh

PI: [name] MPH
Assistant Professor of Medicine
Division of Rheumatology and Clinical Immunology
[name]
[name]
[name]
[contact]

[contact]

[contact]

--

Synopsis

Title	The Effect of Atorvastatin on Microvascular Endothelial Function and Raynaud in Early Diffuse Scleroderma.
Short title	TAMER
Clinical study phase	II
Study objective(s)	The primary objective of this study is to assess the effect of atorvastatin therapy on change in microvascular endothelial function
Test drug(s)	Atorvastatin
Name of active ingredient	Atorvastatin
Dose(s)	40 mg once daily
Route of administration	Oral
Duration of treatment	16 weeks
Reference drug(s)	Placebo
Name of active ingredient	Not applicable
Dose(s)	Matching placebo tablets to atorvastatin 40 mg once daily
Route of administration	Oral
Duration of treatment	16 weeks
Background treatment	Not applicable
Indication	Early diffuse systemic sclerosis with Raynaud phenomenon
Diagnosis and main criteria for inclusion	
 1. Men or women aged 18 years and older 2. Early diffuse SSc defined as: 
 < 3 years from the first symptom attributable to scleroderma Meeting the 2013 the ACR/EULAR classification criteria 3. Raynaud phenomenon 4. No use of lipid lowering medication within 60 days of trial entry. 5. women of childbearing potential must have a negative serum pregnancy test at the screening visit.
Study design	Randomized (1:1), double-blind, placebo-controlled, parallel-group, single-center study

Methodology	This study is designed to investigate the efficacy and safety of atorvastatin 40 mg once daily in patients with early diffuse SSc on microvascular endothelial function and clinical Raynaud symptom.
Type of control	Placebo
Number of subjects	30 randomized subjects
Primary variable	Change in microvascular endothelial function as measured by EndoPAT
Plan for statistical analysis	An intention to treat analysis will be performed including all who receive one dose of drug. Initial analysis will describe the baseline population, sociodemographic and clinical characteristics, and compare by treatment group. Means of continuous measures will be conducted using a t-test or Wilcoxon test and discrete measures compared with a chi-square test. The goal of all trial analyses is to provide effect size estimates for design of a later phase 3 clinical trial for statin therapy in early diffuse SSc. The means of EndoPAT for the two groups will be calculated and a 95% confidence interval of the difference of the means will be generated. A t-test will be used to compare the mean levels between the two groups.

Table of contents

1. Introduction	7
1.1 Background	7
1.1.1 Scleroderma (systemic sclerosis)	7
1.1.2 Atorvastatin	8
1.1.3 Mechanism of Action	8
1.2 Rationale of the study	8
2. Study objectives	9
3. Investigators and other study personnel	9
4. Study design	10
4.1 Design overview	10
5. Study population	11
5.1 Eligibility	11
5.1.1 Inclusion criteria	11
5.1.2 Exclusion Criteria	12
5.1.3 Justification of selection criteria	13
5.2 Withdrawal of subjects from study	13
5.2.1 Withdrawal	13
5.2.2 Replacement	14
5.3 Subject identification	14
6. Treatment	14
6.1 Treatments to be administered	14
6.2 Identity of study treatment	14
6.3 Treatment assignment	14
6.4 Dosage and administration	14
6.4.1 Selection of doses in the study	14
6.5 Blinding	15
6.6 Drug logistics and accountability	15
6.7 Post-study therapy	15
6.8 Prior and concomitant therapy	15
7. Procedures and variables	17
7.1 Schedule of procedures	17
7.1.1 Tabulated overview	18
7.1.2 Timing of assessments	19
7.1.2.1 Visit 0 – Screening	19
7.1.2.2 Visit 1 – Baseline (Day 0, Week 0)	19
7.1.2.3 Visit 2: 8 weeks	20
7.1.2.4 Visit 3: 16 weeks (end of study)	20
7.1.2.5 Premature discontinuation of study drug treatment	21
7.2 Population characteristics	21
7.2.1 Demographic	21
7.2.2 Medical history	21
7.3 Efficacy	21

7.4	Pharmacokinetics / pharmacodynamics	22
7.5	Safety	22
7.5.1	Adverse events.....	22
7.5.1.1	Definitions.....	22
7.5.1.2	Classifications for adverse event assessment.....	23
7.5.1.2.1	Seriousness.....	23
7.5.1.2.2	Intensity.....	23
7.5.1.2.3	Causal relationship.....	24
7.5.1.2.4	Action taken with study treatment	24
7.5.1.2.5	Outcome	25
7.5.1.3	Assessments and documentation of adverse events	25
7.5.1.4	Reporting of serious adverse events	25

1.1 Background

1.1.1 Scleroderma (systemic sclerosis)

Systemic sclerosis (SSc) is an uncommon disease, however has the highest case specific mortality of any of the rheumatic disease. The features of this disease include chronic, fibrosing, autoimmune responses characterized by small vessel vasculopathy, autoantibody production, and fibroblast dysfunction leading to increased deposition of extracellular matrix.¹

Systemic sclerosis is further divided into two subtypes defined by the extent of skin involvement: limited cutaneous systemic sclerosis and diffuse cutaneous systemic sclerosis². According to LeRoy and colleagues, classification to limited or diffuse disease is based on the extent of skin tightening³. In limited disease skin tightening is confined to the fingers, hands, and forearms distal to the elbows, with or without tightening of skin of the feet and of the legs distal to the knees. Proximal extremities and the trunk are not involved. In dcSSc, the skin of the proximal extremities and trunk is also involved. Both diffuse and limited SSc are associated with internal organ involvement; however, patients with diffuse SSc are at greater risk for clinically significant major organ dysfunction.

SSc is an orphan disease with an estimated US prevalence of 276 patients /10⁶ ⁴.

Vascular burden in SSc: Raynaud's phenomenon (RP) is an almost universal manifestation of SSc, with 95% of all patients being affected. The burden of SSc-associated vascular complications is high, with up to 65% of patients experiencing DU, 10% gangrene or amputation, 15% renal crisis, 15% pulmonary hypertension and 17% peripheral vascular disease^{5 6}. The progression of microvascular and macrovascular abnormalities in SSc and their associated complications are not well described. Thus, we are unable to predict which patients will develop severe vascular complications. Moreover, there are no FDA-approved therapies for SSc-associated Raynaud phenomenon and DU. Identifying a therapy that diminishes or prevents the progression of SSc vasculopathy and complications would significantly improve outcomes, and increase our understanding of the underlying mechanistic abnormalities⁷.

The goal of the current pilot study is to evaluate the efficacy and safety of a 16-week treatment with atorvastatin vs. placebo in patients with early diffuse SSc and Raynaud phenomenon.

1.1.2 Atorvastatin

1.1.3 Mechanism of Action

Atorvastatin is a HMG coenzyme-inhibitor, which was FDA approved in 1996. Atorvastatin is a hydrophobic statin with the ability to enter endothelial cells and has a long history of safety in multiple diseases, including prior use in SSc patients. Atorvastatin has been shown in other rheumatic diseases (rheumatoid arthritis, lupus, Behçet disease) to improve endothelial function and disease activity⁸⁻¹⁰ and is available in a generic form.

1.2 Rationale of the study

Raynaud phenomenon affects 95% or more of patients with SSc. Unfortunately, there are no drugs approved in US for the treatment of Raynaud phenomenon. Raynaud is felt to represent the earliest signs of microvascular endothelial dysfunction in SSc.

Statins have beneficial pleiotropic effects on the vasculature and may modify all three aspects of the SSc disease process. Statins are known to improve endothelial function by increasing nitric oxide (NO) production (vasculopathy), down-regulating vascular adhesion molecules that subsequently inhibit lymphocyte migration from the vasculature (immune system activation)¹, and inhibiting overproduction of matrix components (fibrosis)^{3 11 12}. Given these mechanisms, statins have the potential to improve vascular dysfunction and abnormalities in SSc.

Five small studies have examined the effect of statins on Raynaud and DU with mixed results^{10 13-16} in predominantly later disease SSc, when the vasculopathy may not have been amenable to intervention, and have assessed macrovascular endpoints such as brachial flow-mediated dilation (FMD) for a microvascular disease. Of the five studies, two small placebo controlled randomized trials of atorvastatin. The lower dose study (atorvastatin 20 mg daily for 8 weeks) was negative but used patients with late disease (up to 47 years). The higher dose study (40 mg daily) was positive, but also using late disease patients and found an increase in brachial FMD as a positive outcome. No studies have evaluated the effect of statins on microvascular endothelial function in SSc, although this is the primary vasculature affected in Raynaud phenomenon and early SSc. In our preliminary work in early SSc patients, arteriole-level microvascular changes appear attenuated by statin use (40% with abnormal EndoPAT in statin users versus 100% in non-statin users, $p=0.03$). Based on this, we propose that early statin intervention will improve microvascular endothelial function and thus reduce Raynaud activity.

Benefit-risk assessment

There are currently no disease-specific pharmacotherapies approved for Raynaud phenomenon. Considering the mechanism of action and pleiotropic effects of atorvastatin we believe the potential benefits of atorvastatin include:

- Improvement of microvascular endothelial function
- Decrease severity of Raynaud's attacks.

- Improvement of microcirculatory flow as evaluated by laser speckle contrast imaging
- Improvement of macrovascular endothelial function as evaluated by brachial flow-mediated dilation.
- Taking into account the seriousness of the disease as well as the medical need for an effective and safe therapy, on balance the expected benefit to subjects with this condition outweighs potential risks.

2. Study objectives

The primary objective of this study is to assess the effect of atorvastatin therapy on change in microvascular endothelial function as measured by EndoPAT technology.

The secondary objectives of this study are to assess the efficacy and safety of treatment with atorvastatin 40 mg once daily as follows:

Secondary objectives

- Change in Raynaud symptoms
- Change in microcirculatory flow assessed by laser speckle contrast imaging
- Change in macrovascular function assessed by brachial FMD
- SHAQ and PROMIS
- To assess serum biomarkers
- To assess EPCs.
- To assess nitrite analysis

3. Investigators and other study personnel

Principal investigator:

[name] MD MPH
University of Pittsburgh
[name]
[name]
[name]
[contact]

Research coordinators:

[name] CCRC and [name] BS
University of Pittsburgh
[name]
[name]
[name]
[contact]
[contact]
[contact]
[contact]

Data Manager: [name] [name]
University of Pittsburgh

[name]
 [name]
 [name]
 [contact]

Study Statisticians: [name] and
 [name]
 [name]
 [name]
[contact]
[contact]

External data evaluation bodies

An independent safety monitor will provide safety oversight.

4. Study design

[figure not shown]
4.1 Design overview

In this single-center, (1:1), double-blind, placebo-controlled, parallel-group study, a total of 30 subjects are planned to be randomized (approximately 15 subjects to the atorvastatin group and 15 to the placebo group).

The study design consists of a single 16 week study treatment phase

- **Screening phase:** up to 4 weeks
- **Main Study Treatment phase:** 16 weeks of double-blind treatment
- **Termination Visit and Safety follow-up visit:** A termination visit and a safety follow-up visit will take place for all patients who discontinue study drug or withdraw from the study.

Figure 4-1: Study Design

4.1.1 Screening phase (up to 4 weeks)

After signing the informed consent document, subjects will undergo a screening to include baseline labs (creatinine and LFTs) and review of the inclusion/exclusion criteria. Screening

and baseline can occur on the same day if clinical labs (creatinine and LFTs) have been drawn as part of routine care within 28 days of the baseline.

4.1.2 Study Treatment phase (Week 0 to Week 16)

At the baseline (week 0) visit, subjects who have met all of the inclusion and none of the exclusion criteria will be randomized using a 1:1 randomization scheme that will be regulated centrally through the UPMC IDS. Each patient enrolling in the study will be assigned an ID. At week 0 patients will undergo assessment of Raynaud activity/severity and noninvasive vascular imaging.

Patients will have a visit at week 8 to assess safety, tolerability and adverse effects of the study drug. Raynaud activity/severity and DU will be assessed.

Patients will have a final end of study visit at week 16 to assess safety, tolerability and adverse effects of the study drug. They will also undergo assessment of Raynaud activity/severity and noninvasive vascular imaging.

Dose Interruptions

If treatment is interrupted for any reason the following rules should be applied:

- ≤ 14 consecutive days without treatment it is at the discretion of the investigator if the study medication can be restarted
- >14 consecutive days without treatment: withdraw the subject from study medication.

4.1.3 Termination Visit and Safety Follow-up Visit

A termination visit and a safety follow-up visit (30 days after last dose of study medication) should be performed for only those patients who withdraw or discontinue study drug before the completion of the trial at 16 weeks.

In all other patients a follow-up phone call at 30 days will be used to assess and follow-up on adverse events.

A detailed schedule of evaluations is presented in Sections 7.1.1 and 7.1.2.

5. Study population

5.1 Eligibility

5.1.1 Inclusion criteria

Subjects must meet the following criteria to be eligible for enrollment in the study:

1. Written informed consent
2. Men or women age 18 -70 years
3. Systemic sclerosis, as defined by ACR/EULAR 2013 criteria¹⁷ with disease duration of less than 3 years from the first symptom attributable to SSc.

4. Raynaud phenomenon.
5. No use of lipid-lower medication within 60 days.
6. Ability to comply with the clinical visits schedule and the study-related procedures

5.1.2 Exclusion Criteria

Subjects who meet any of the following criteria will be excluded from enrollment in the study:

- Medical and surgical history
 - History of known cardiovascular disease or myocardial infarction
 - History of stroke
 - Diabetes mellitus
- Hepatic-related criteria
 - Hepatic insufficiency classified as Child-Pugh C
 - Elevated liver enzymes > two times normal at screening
- Renal-related criteria
 - Estimated glomerular filtration rate (eGFR) < 30 mL/min/1.73m² (MDRD formula), creatinine > 2.0 mg/dL or history of scleroderma renal crisis at the screening visit
- Known allergy or adverse reaction to atorvastatin or another statin drug
- Laboratory examinations
 - Subjects with elevated CPK (greater than two times normal) at screening.
- Prior and concomitant therapy
 - Concomitant use of calcium channel blockers or angiotensin receptor blockers are allowed, provided the participant has been on a stable dose for four weeks or longer at the time of randomization.
 - Concomitant therapy with prostacyclin analogs.
 - nitrates or NO donors (such as amyl nitrate) in any form, including topical; phosphodiesterase (PDE) 5 (PDE5) inhibitors (such as sildenafil, tadalafil, vardenafil); and nonspecific PDE5 inhibitors (theophylline, dipyridamole)
 - concomitant use of strong inhibitors of CYP 3A4 to include: clarithromycin, protease inhibitors, itraconazole, cyclosporine, gemfibrozil or other fibrates, niacin, rifampin, digoxin.
- Other
 - Pregnant women or breast feeding women

- Women of childbearing potential not willing to use adequate contraception (as defined in the aforementioned inclusion criteria, Section 5.1.1) and not willing to agree to pregnancy testing at weeks 8 and 16.
- Smoking or tobacco use within four weeks of screening.
- Any other condition or therapy that would make the subject unsuitable for this study and will not allow participation for the full planned study period

Note: One re-assessment of laboratory parameters is allowed during the screening phase to re-assess the eligibility of subjects.

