7.1.2 Timing of assessments

Screening and baseline visits can occur on the same day.

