7.1.2.1 Visit 0 – Screening

Screening evaluations will occur after the subject has provided written informed consent. The following evaluations will be performed and information obtained up to 28 days before randomization and the start of study drug treatment:

- Patient information and obtaining of written informed consent
- Eligibility: Assessment of inclusion and exclusion criteria (see Section 5.1)
- Demographic data, including age, gender and ethnicity.
- Complete medical history
- Liver function tests and creatinine with GFR. Labs obtained as part of routine clinical care up to 28 days prior to screening will be accepted.

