7.1.2.2 Visit 1 – Baseline (Day 0, Week 0)

The following assessments will be performed at the Baseline visit (Day 0 of study drug treatment):

- Reconfirmation of eligibility (assessment of inclusion/exclusion criteria; Section 5.1), if performed at separate visits
- Cardiovascular history and assessment or risk factors
- Physical Exam
- Assessment of Raynaud and digital ulcer activity and severity (questionnaire)
- Digital ulcer assessment
- Questionnaires
 - SHAQ
 - PROMISE-29
- Vital signs (blood pressure, heart rate, height, weight).
- Vascular Imaging (to be performed simultaneously)
 - EndoPAT
 - Laser speckle contrast imaging
 - Brachial FMD
- Pregnancy test (urine) for all women of childbearing potential (see Section 7.5.2)
- Blood samples for safety (LFTs, creatinine with GFR, CPK)
- Blood sample for biomarkers
- Blood sample for nitrite analysis

- Recording and assessment of AEs (see Section 7.5.1)
- Concomitant therapy
- Randomization to atorvastatin or placebo (see Section 6)
- Dispense study drug

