7.5.1.5 Adverse events

7.5.1.6 Expected adverse events, and events of special safety interest

Common expected adverse events include: myalgias/artralgias (> 10%), diarrhea (5-14%), nasopharyngitis (4-13%), and dyspepsia (3-6%).

There are four significant adverse events associated with the use of atorvastatin which include 1) increase in fasting blood glucose in patients with diabetes mellitus; 2) hepatotoxicity; 3) rhabdomyolysis; and 4) the very rare event of immune-mediated necrotizing myopathy. Diabetes mellitus is an exclusion criteria for this study.

In regards to hepatotoxicity, elevated serum transaminases have been reported in as high as 2-3% of patients taking a higher dose of atorvastatin (80 mg once daily), although postmarketing reports of hepatic failure are rare. These will be monitored at baseline, week 8 and week 16. We will discontinue if hepatic enzymes are > three times the upper limit of normal.

Many patients receiving HMG-CoA reductase inhibitors experience myalgias, and this is an expected adverse event. Patients receiving HMG-CoA reductase inhibitors have developed rhabdomyolysis with acute renal failure and/or myopathy. This risk is dose-related and is increased with concurrent use of CYP3A4 inhibitors (eg, clarithromycin, protease inhibitors), fibric acid derivatives (eg, gemfibrozil), or niacin (doses ≥ 1 g/day) (see Drug Interactions), which will be monitored. Serum CPKs will be checked at baseline, week 8 and week 16. We will advise patients not to perform unusual or heavy bouts of exercise in the 24 hours before visits. We will discontinue in any patient in which CPK levels are markedly elevated (> 5 times ULN) or if myopathy is suspected/diagnosed. Patients will be instructed to report unexplained muscle pain, tenderness, weakness, or brown urine. If they develop any of these symptoms, they will return for an interval visit with repeat CPK and exam at that time.

Patients receiving HMB-CoA reductase inhibitors have also been rarely reported to develop an immune-mediated necrotizing myopathy (IMNM). IMNM presents as proximal muscle weakness with elevated CPK levels, which persists despite discontinuation of HMG-CoA reductase inhibitor therapy. Serum CPKs will be checked at baseline, week 8 and week 16. We will discontinue in any patient in which CPK levels are markedly elevated (>5 times ULN) or if myopathy is suspected/diagnosed.

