7.5.3 Vascular Assessments

Prior to beginning vascular testing, all patients will rest for 15 minutes in a quiet, dark and temperature-controlled room (set at 77 degrees Fahrenheit or warmer). Measurement of EndoPAT™, LSCI and brachial FMD will be performed simultaneously. Measurements will be obtained before and after vascular occlusion for all studies to assess endothelial dependent vasodilation. LSCI and brachial FMD will then be performed before and after administration of 0.4 mg of sublingual NTG to assess endothelial-independent vasodilation.

During the acclimation period a pneumatic cuff will be placed on the subject's right arm. Once the acclimation period has ended, a baseline pulse and flow measurements will then be obtained for 5 minutes for all modalities. Following this vaso-occlusion will be induced by inflating the pneumatic cuff to a pressure of 280 mmHg or 60 mmHg higher than systolic blood pressure (whichever was the highest), for 5 minutes. After 5 minutes the cuff will be rapidly deflated and measurements will be obtained for an additional 5 minutes. Subjects will then receive a single 0.4 mg sublingual spray of NTG. We will then obtain measurements as detailed in the individual vascular studies below over a period of 10 minutes.

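### CPK above two times normal is a screening exclusion, but the first scheduled CPK is drawn at the randomisation visit and nothing requires its result first

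*Combined protocol and SAP*

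**What the plan says.** Section 5.1.2 ties three laboratory-value exclusions to screening. The hepatic one is "Elevated liver enzymes > two times normal at screening", the renal one concerns eGFR and creatinine, and the muscle one is "Subjects with elevated CPK (greater than two times normal) at screening". A note to 5.1.2 allows one repeat of laboratory values, during the screening phase.

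The screening visit in 7.1.2.1 lists "Liver function tests and creatinine with GFR" and no other blood test. Section 7.1.2 states that "Screening and baseline visits can occur on the same day". Section 4.1.1 gives the condition for this: screening "and baseline can occur on the same day if clinical labs (creatinine and LFTs) have been drawn as part of routine care" in the 28 days before baseline.

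The baseline list in 7.1.2.2 has a safety blood sample that includes CPK, followed further down by randomisation and dispensing. Eligibility appears there as "Reconfirmation of eligibility (assessment of inclusion/exclusion criteria; Section 5.1), if performed at separate visits". Section 6.6 has the whole supply handed out at that visit. Sections 4.1.2 and 6.3 require that all eligibility criteria be satisfied for randomisation. On study, 5.2.1 and 7.5.1.6 stop treatment when CPK exceeds 5 times the upper limit of normal.

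**The concern.** An exclusion can only work if its value is known before the patient is randomised. For CPK the protocol sets the threshold but schedules no test that would supply the value in time. A site could complete every listed screening procedure, randomise, dispense 16 weeks of tablets, and only then receive the first CPK result.

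The criterion bears on a recognised risk of the drug. Section 7.5.1.6 says "There are four significant adverse events associated with the use of atorvastatin", and two of the four are muscle events: rhabdomyolysis and immune-mediated necrotizing myopathy. What is at stake is patient safety and the integrity of the eligibility check. The primary analysis is not affected.

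**Working it through.** The plan gives no figure to reproduce here. The check sets side by side every place that puts CPK or screening bloods in time.

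**1. Which laboratory exclusions have a screening test?**

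| Exclusion in 5.1.2 | 4.1.1 | 7.1.1, Screening column | 7.1.2.1 |
|---|---|---|---|
| Liver enzymes | Named | Marked | Named |
| eGFR/creatinine | Creatinine named | Marked | Named |
| CPK | Not named | Blank | Not named |

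Two of the three have a scheduled screening test, and CPK is the exception. The three sections agree, so this does not depend on one table that might have been damaged in conversion.

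**2. When is CPK first drawn?** Sections 7.1.1 and 7.5.1.6 both give baseline, week 8 and week 16, and the visit lists in 7.1.2.2 to 7.1.2.4 match. That is 3 scheduled draws, of which 0 fall before the Day 0 visit.

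**3. Is there a step that waits for the result?**
- Sections 4.1.2 and 6.3 state the general requirement but name no test and no wait.
- Section 7.1.2.2 lists the blood samples ahead of randomisation. That order fits a draw before randomisation, but drawing a sample does not give a result.
- With separate visits, eligibility is reconfirmed at the same visit at which the first CPK is drawn.
- With same-day entry, the reconfirmation item does not apply, and the prior results required are creatinine and liver tests only.

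**4. Does the answer depend on whether Day 0 counts as screening?**
- If it does not, the CPK exclusion has no scheduled measurement at all, and the single repeat in 5.1.2 has no scheduled CPK to act on.
- If it does, as can be argued for same-day entry, the measurement exists but its result need not be available before randomisation.

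The text needs changing on either reading.

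**5. What catches the patient afterwards?** Take two times normal and 5 times the upper limit of normal as multiples of the same limit (an assumption, since 5.1.2 does not say upper limit). The exclusion then covers values above 2, and the numeric stopping rule covers values above 5. A value above 2 and up to 5 lies over the entry limit but triggers no numeric rule. What remains is withdrawal on the investigator's judgement (5.2.1), stopping for suspected or diagnosed myopathy, and an extra CPK if symptoms appear (7.5.1.6). None of these is tied to a raised value in a patient without symptoms.

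**The case against.** The strongest reply is that the protocol already has the gate. Sections 4.1.2 and 6.3 apply on both entry routes, so randomising with CPK unknown would breach the protocol, and a careful site would wait. The order of the Day 0 list supports that reading. Section 4.1.1 also describes the screening bloods as baseline labs, so the two terms are used loosely. The manual of procedures (7.5.1.8) and the Safety Monitoring Plan (8.2.3) are not among the documents and may contain a hold rule. All of this stands, and it rules out any claim that the protocol permits ineligible patients to be randomised. It does not remove the mismatch: a general gate cannot be applied to a value that the schedule does not deliver in time, and a hold rule elsewhere would still leave 5.1.2 and 7.1.1 in disagreement.

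A reader might infer that a patient would spend about half the course on atorvastatin with CPK unknown, because the next scheduled draw is at 8 × 7 = 56 days, ±7, so 49 to 63 days after Day 0. The documents do not support this. That interval is the time to the next scheduled draw. The Day 0 result would be seen once reported, and the investigator could act on it. With 1:1 allocation, about half of such patients would be on placebo.

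A reader might also infer that any Day 0 value above 2 times normal plainly meets the exclusion. Under separate visits that holds only if Day 0 counts as screening, which the wording of 5.1.2 does not settle.

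**Conclusion.** Wrong as written: the eligibility criterion and the visit schedule conflict. Following the schedule, a patient with CPK above 2 and up to 5 times normal could be randomised and dispensed drug or placebo before the result is known. Any action after that would rest on judgement, suspected myopathy or symptoms. Above 5 times the upper limit, the withdrawal rule would apply once the result was reported.

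The size is structural: one of three screening laboratory exclusions has no screening test, and none of three scheduled CPK draws precedes the randomisation visit. The documents do not show how many patients would fall in the band, or that any did, and no estimate is made. Confidence is high for the mismatch. It is lower for the safety consequence, which depends on how fast results return and on operating documents not available here. The point should be fixed, but it does not touch the sample size, endpoint or analysis.

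**What to change.** **Preferred.** Add CPK to the screening bloods in 4.1.1, 7.1.1 and 7.1.2.1, and to the routine-care results (within 28 days of baseline) that same-day entry requires. A value then exists before randomisation, and the one repeat allowed in 5.1.2 can apply to it. The cost is one analyte. Patients relying on routine bloods without a CPK would need a new draw, and those without a recent CPK would lose the same-day option.

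**Alternative.** Reword 5.1.2 so that the CPK limit applies at screening or baseline, before randomisation. State in 4.1.2 and 7.1.2.2 that randomisation and dispensing wait for the Day 0 result, and extend the repeat to that result. Only this option also covers a patient who is normal at screening but raised on Day 0. It needs no extra test, but it may need a second visit and may separate the first dose from the baseline vascular studies. A patient then excluded could already have had the full imaging session, including nitroglycerin: "Subjects will then receive a single 0.4 mg sublingual spray of NTG" (7.5.3).

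Leave the 2-times and 5-times thresholds as they are under either option.
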